- Time to confirmed undetectable RSV RNA viral load (days) is defined as the time between the date of first dose to the first 2 consecutive post-baseline time points of

achieving RSV RNA viral load TND. Subjects with baseline RSV viral load TND will be excluded from the analysis.

Frequency counts and percentages of subjects by end of study (Day  $28 \pm 4$ ), and their respective 95% CIs will be reported using Clopper Pearson CI methods for the following endpoints summarized using the Efficacy Population.

- Proportion of hospitalized subjects requiring oxygen supplementation or have an increased oxygen requirement.
  - Subjects who are hospitalized at randomization and/or during study are included. The
    proportion will be defined by the number of subjects who develop a new requirement for
    oxygen supplementation or new increase(s) in oxygen requirements after the first dose of
    study drug, based on the response of "yes" to the "is this an increase of oxygen
    supplementation compared to previous use?" question on the Oxygen Supplementation
    CRF.
- Proportion of hospitalized subjects requiring mechanical ventilation
  - Subjects who are hospitalized at randomization and/or during study are included. The proportion will be defined by the number of subjects who developed a new requirement for mechanical ventilation after the first dose of study drug. Subjects on mechanical ventilation prior to the first dose of study drug are excluded from analysis.
- Deaths among hospitalized subjects
  - Subjects who are hospitalized at randomization and/or during study are included.
- Proportion of outpatients who are subsequently hospitalized or died
  - $\circ$  Subjects who are not hospitalized at randomization are included.
- Proportion of outpatients who died
  - Subjects who are not hospitalized at randomization are included.

The following endpoints will be summarized using the Efficacy Population. The summary statistics will include, at a minimum, the number of non-missing measurements, mean, standard deviation, median, minimum, 25th percentile, 75th percentile, and maximum.

- Time to discharge for hospitalized subjects
  - Time to first hospital discharge for subjects who are hospitalized at randomization will be defined as the time between the first dose of study drug and the first date of discharge. For subjects with continuous hospitalization, the last date of discharge from the continuous hospitalization will be used.

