- Time to use of oxygen for hospitalized subjects who are not receiving oxygen at the time they receive the first dose of study drug
  - For subjects who are hospitalized at randomization, time to use of oxygen for hospitalized subjects not receiving oxygen at the time they receive the first dose, is

defined as the time between the date/time of first dose of study drug to the first date/time of receiving oxygen.

- Duration of oxygen use for hospitalized subjects
  - This analysis will include subjects who are hospitalized at randomization and received oxygen supplementation at any time after the first dose of study drug. The duration of oxygen use (days) is defined as the sum of each duration of oxygen use (days) that occurred from the first dose of study drug to the end of study. The duration of oxygen use for the initial hospitalization is calculated as date/time of the end of oxygen use – date/time of first dose of study drug. The duration of oxygen use for subsequent rehospitalization(s) is calculated as date/time of the end of oxygen use – date/time of the start of oxygen use for the rehospitalization. Missing start times will be imputed to 00:01. Missing end times will be imputed to 23:59.
- Time to mechanical ventilation for hospitalized subjects
  - This analysis will include subjects who are hospitalized at randomization and required mechanical ventilation at any time after the first dose of study drug. Subjects on mechanical ventilation before their first dose of study drug are excluded from analysis. Time to mechanical ventilation is defined as the date/time from the first dose of study drug to the first use of mechanical ventilation.
- Duration of mechanical ventilation for hospitalized subjects

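### The oxygen, ventilation and death proportions count children admitted after dosing as hospitalized, so part of each denominator depends on an event that the SAP treats as an efficacy outcome

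*SAP*

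**What the plan says.** SAP 4.13.4 reports several clinical proportions to end of study (Day 28 ± 4) as counts, percentages and Clopper-Pearson intervals in the Efficacy Population. Three of them, the oxygen proportion, the ventilation proportion and "Deaths among hospitalized subjects", carry the rule "Subjects who are hospitalized at randomization and/or during study are included". The oxygen numerator counts a new need for "oxygen supplementation or new increase(s) in oxygen requirements after the first dose of" study drug; ventilation likewise must be new after the first dose.

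The same section lists "Proportion of outpatients who are subsequently hospitalized or died", as well as outpatient deaths, both over children not hospitalized at randomization. Time to hospitalization of initial outpatients is a further secondary endpoint.

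The related time and duration endpoints use another starting group:

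- Discharge: "Time to first hospital discharge for subjects who are hospitalized at randomization will be defined as the time between" first dose and discharge.
- Time to oxygen: "For subjects who are hospitalized at randomization, time to use of oxygen for" those not on oxygen at first dose.
- Duration of oxygen: "This analysis will include subjects who are hospitalized at randomization and" received oxygen after the first dose.
- Time to ventilation: "This analysis will include subjects who are hospitalized at randomization and required mechanical ventilation at any time after the first dose of study drug". Duration of ventilation starts from the same group.

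Protocol 2.2.2 says only that these endpoints concern hospitalized subjects; it does not say when that status is taken. SAP 4.13.5 repeats the Part 2 definitions on pooled data. The sensitivity analyses in SAP 4.13.6 (final dose, steroids, coinfection) do not include these proportions on the group hospitalized at randomization.

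**The concern.** Children hospitalized at randomization form a subgroup fixed before treatment, so the arms can be compared within it. Outpatients who join the denominator later are selected by an event that treatment may influence and that the SAP lists as an efficacy outcome. If the drug prevents admissions, the EDP-938 denominator becomes smaller than it would otherwise have been, and the admitted outpatients may be a more or less severe selection than those on placebo. The proportion then mixes the risk in baseline inpatients, the admission rate, and the severity of those admitted. A reader of the table cannot separate these or tell which way the mixture has moved the comparison.

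The SAP also ends up with two meanings of hospitalized within one section: at randomization for the oxygen and ventilation time and duration endpoints, and at randomization or later for the oxygen and ventilation proportions.

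**Working it through.** **Planned numbers.** SAP 4.2 plans 12 children per cohort and age group in Part 1 and 20 per age group in Part 2: 2 × 2 × 12 + 2 × 20 = 88, consistent with the stated figure of approximately 90. With 2:1 and 4:1 allocation (SAP 2.1, 2.2), and Cohort 2 taken as 8:4, EDP-938 has 4 × 8 + 2 × 16 = 64 and placebo 4 × 4 + 2 × 4 = 24. Part 2 alone has 32 and 8.

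**Assumed inputs.** The documents give no inpatient share, admission rate or oxygen rate, so all of these are assumptions:

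- s, share hospitalized at randomization: 25%, 50%, 75%
- r, oxygen risk in those children: 30% in both arms
- a, admission rate among outpatients: 30% placebo, 15% EDP-938
- o, oxygen risk once admitted: set by scenario
- outpatients who are never admitted receive no oxygen

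**Formula.** SAP proportion = [s·r + (1 − s)·a·o] / [s + (1 − s)·a].

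**Scenario B: oxygen risk per child equal in both arms.** The drug prevents only admissions that would not need oxygen: o = 50% placebo, 100% EDP-938. At s = 25%:

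- placebo: (0.075 + 0.75 × 0.30 × 0.5) / (0.25 + 0.225) = 0.1875 / 0.475 = 39.5%
- EDP-938: (0.075 + 0.75 × 0.15 × 1.0) / (0.25 + 0.1125) = 0.1875 / 0.3625 = 51.7%

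**Scenario A: o = 80% in both arms.** **Scenario C: admission 30% and o = 80% in both arms.**

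| s | B: placebo vs EDP-938 | Difference | A: placebo vs EDP-938 | Difference | C: difference |
|---|---|---|---|---|---|
| 25% | 39.5% vs 51.7% | +12.3 | 53.7% vs 45.5% | −8.2 | 0 |
| 50% | 34.6% vs 39.1% | +4.5 | 41.5% vs 36.5% | −5.0 | 0 |
| 75% | 31.8% vs 33.3% | +1.5 | 34.5% vs 32.4% | −2.2 | 0 |

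Differences are EDP-938 minus placebo, in percentage points.

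**The same scenarios on fixed denominators.**

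- Hospitalized at randomization: 30% vs 30% in every row.
- All outpatients at randomization, a·o: B gives 0.30 × 0.5 = 15% vs 0.15 × 1.0 = 15%; A gives 0.30 × 0.8 = 24% vs 0.15 × 0.8 = 12%.
- All dosed children, s·r + (1 − s)·a·o: B gives equal risks in the two arms (18.8%, 22.5%, 26.2% for the three values of s); A gives 25.5% vs 16.5%, 27.0% vs 21.0% and 28.5% vs 25.5%.

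In B the apparent harm comes entirely from the denominator. In A the drug does lower oxygen need, but only among outpatients; the SAP figure shows it in a group described as hospitalized and slightly understates the all-dosed difference (−8.2 against −9.0 points at s = 25%).

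**Size of the denominators.** With pooled numbers and s = 50%, the fixed denominators are 12 and 32; the SAP rule gives 24 × 0.65 = 15.6 and 64 × 0.575 = 36.8. In Part 2, placebo has 8 children in total. With 4 of them in the denominator, one event is 25% (exact 95% interval 0.6% to 80.6%), so a single late admission visibly moves the figure.

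The formula applies equally to ventilation and death; I assumed no rates for those.

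**The case against.** **Descriptive only.** SAP 4.2 plans no formal testing for Parts 1 or 2, and the pooled inferential analyses in SAP 4.13.5 cover viral and symptom endpoints, not these proportions. This stands: no error rate, power figure or primary conclusion is affected.

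**Partly covered already.** Outpatient deaths, and outpatients hospitalized or dead, are reported over all outpatients, so an effect on admission would be visible nearby. This stands too. What lacks a fixed denominator is outpatient oxygen and ventilation, and the three inpatient proportions themselves.

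**The time endpoints are not a perfect model.** Time to oxygen leaves out children already on oxygen, whereas the proportion counts increases among them. Time to ventilation includes only children who went on to be ventilated. Deaths have no time endpoint. A reader might infer that a common denominator would make every proportion match a time endpoint; it would not. The narrower point remains that the SAP uses two starting definitions of hospitalized.

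**The rule fits the protocol.** Protocol 7.1 takes hospitalization status on the day of the visit. That rule is for study assessments and does not define an endpoint denominator.

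**Planned admissions.** Inclusion criterion 6 lets Part 1 Cohort 1 Age Group 2 children enter with admission already planned. Their later admission is not a treatment outcome, and a strict at-randomization rule could drop them. This stands and belongs in the fix; it matters for the pooled tables, since these endpoints are not specified for Part 1 alone.

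**A stronger reading.** A reader might infer that any difference in these tables is an artefact and that the baseline-inpatient figure is the whole randomized comparison. Scenario A shows otherwise: that subgroup alone would miss a real benefit in outpatients, which is why the outpatient rows are needed.

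**Conclusion.** The point holds for all three proportions. Part of each denominator is set after dosing by an event that the SAP counts as an efficacy outcome, and the rule carries into the pooled analysis without a supporting analysis on the group hospitalized at randomization. Under the assumed rates, the oxygen comparison moves by 1.5 to 12.3 points against the drug with equal risk per child, or by 2.2 to 8.2 points in its favour with 80% oxygen use after admission. The shift grows as the outpatient share rises and vanishes if treatment changes neither the rate nor the severity mix of admissions. These sizes are illustrations: no rate in them comes from the documents. The consequence is limited to how descriptive secondary tables are read. The documents do not show that a distortion will occur, only that the definition allows one in an unpredictable direction.

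**What to change.** In SAP 4.13.4, and through it 4.13.5:

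1. Restrict the oxygen, ventilation and death proportions to children hospitalized at randomization.
2. State how Part 1 Cohort 1 Age Group 2 children whose admission was already planned at entry are classed, using only information recorded before the first dose.
3. For outpatients at randomization, add new oxygen and new ventilation requirement over all dosed outpatients, next to the existing rows for death and for hospitalization or death.
4. If wanted, keep the current at-randomization-or-later version as supportive and label it so.

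The cost is SAP wording and two further table rows. The analyses use data already planned for collection, and no event is lost. Protocol 11.2 allows SAP changes only before unblinding, so the edit has to be made by then.

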# Secondary Endpoints

• Safety and tolerability of EDP-938 compared to placebo as assessed by, but not limited to, AEs, vital signs, and clinical laboratory results;

- AUC for RSV RNA viral load measured in nasal swab samples by RT-qPCR;
- Proportion of subjects with RSV RNA viral load below the LOD in subjects receiving EDP-938 compared to placebo;
- Time to RSV RNA viral load being undetectable;
- PK parameters of EDP-938 including AUC and predose concentrations;
- Time to discharge for hospitalized subjects;
- Time to use of oxygen for hospitalized subjects who are not receiving oxygen at the time they receive the first dose of study drug;
- Proportion of hospitalized subjects requiring oxygen supplementation or have an increased oxygen requirement;
- Time to mechanical ventilation for hospitalized subjects;
- Proportion of hospitalized subjects requiring mechanical ventilation;
- Deaths among hospitalized subjects;
- Time to hospitalization for initial outpatients who are subsequently hospitalized;
- Proportion of outpatients who are subsequently hospitalized or died;
- Time to resolution of symptoms for outpatients who are not hospitalized.

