  - This analysis includes subjects who are hospitalized at randomization and required mechanical ventilation at any time after the first dose of study drug. The duration of mechanical ventilation (days) is defined as the sum of each duration of mechanical ventilation (days) that occurred from the first dose of study drug to the end of study. The duration of mechanical ventilation for the initial hospitalization is calculated as date/time of the end of mechanical ventilation date/time of first dose of study drug. The duration of mechanical ventilation for subsequent rehospitalization(s) is calculated as date/time of the end of mechanical ventilation date/time of the start of mechanical ventilation. Missing start times will be imputed to 00:01. Missing end times will be imputed to 23:59.
- Time to hospitalization for initial outpatients who are subsequently hospitalized
  - Time to hospitalization for initial outpatients who are subsequently hospitalized will be calculated, defined as the time between the date/time of first dose to the first date of hospitalization.
- Time to resolution of symptoms for outpatients who are not hospitalized
  - Time to resolution of symptoms for outpatients at randomization who are not hospitalized during study, is defined as the time between the date/time of first dose to the first of 2 consecutive time points where each of the seven symptoms assessed by the Parent/Caregiver ReSVinet clinical scoring is 0 or 1. If a subject meets the resolution

definition (0 or 1 score for 2 consecutive timepoints) at baseline and Day 2, then this subject will be excluded from the analysis.

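### For the initial hospitalisation, the SAP counts oxygen and ventilation time from first dose, so a child who starts support later has the support-free wait counted as support

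*SAP*

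**What the plan says.** SAP 4.13.4 summarises duration of oxygen use and duration of mechanical ventilation for children hospitalised at randomisation. The oxygen analysis includes such a child who "received oxygen supplementation at any time after the first dose of study drug". The ventilation analysis has the parallel rule.

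The oxygen paragraph then makes three statements about the variable:

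- **Definition.** Duration "is defined as the sum of each duration of oxygen use (days) that occurred from the first dose of study drug", up to the end of study.
- **Initial hospitalisation.** It "is calculated as date/time of the end of oxygen use – date/time of first dose of study drug". The start of oxygen does not appear.
- **Rehospitalisation.** It is "date/time of the end of oxygen use – date/time of the start of oxygen use for the rehospitalization".

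The ventilation paragraph repeats this structure. The initial stay "is calculated as date/time of the end of mechanical ventilation date/time of first dose of study drug", and a rehospitalisation uses "date/time of the end of mechanical ventilation date/time of the start of mechanical ventilation". The minus signs are missing from the text available for review; I read both as subtractions, by analogy with oxygen.

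The SAP also expects some children to start oxygen after first dose. SAP 3.2.2 lists as a secondary endpoint "Time to use of oxygen for hospitalized subjects who are not receiving oxygen at the time they receive the first dose of study drug".

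**The concern.** The definition and the initial-stay formula are different quantities unless support is already running at first dose and continues without a break. Nothing in 4.13.4 restricts the formula to children in that position.

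For a child who starts oxygen during the initial stay, the hours before oxygen are reported as time to oxygen in one summary and as oxygen use in the next. The distortion is also unhelpful in direction. If treatment delays the need for support without changing its length, the child scores a longer duration. If treatment delays the start and the end time is unchanged, the child has less support but gets no credit.

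At stake is whether a table of days on oxygen, or days ventilated, reports those days. Under 4.13.5 both summaries also carry into the pooled descriptive tables. They are not among the pooled inferential analyses, and the primary endpoint is untouched.

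**Working it through.** The plan states no figure for these durations, so there is none to reproduce. The check compares the SAP's formula with the SAP's definition.

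**Inputs.** The inclusion rule, definition and formulas come from SAP 4.13.4. All timings, proportions and waits below are assumptions, because the documents give no oxygen or ventilation rates.

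**One episode in the initial stay.** Let support run from s to e, in days after first dose, with s at or above 0.

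- Definition: e − s.
- Initial-stay formula: e − 0 = e.
- Overcount: e − (e − s) = s, the whole support-free wait. It is zero when s = 0.

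For a single oxygen episode, s is the child's own value in the time-to-oxygen analysis.

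| Support, days after first dose | Definition | Formula | Overcount |
|---|---|---|---|
| Running at first dose, stops at 2 | 2 | 2 | 0 |
| 1 to 2 | 1 | 2 | 1 |
| 2 to 3 | 1 | 3 | 2 |
| 2 to 5 | 3 | 5 | 2 |
| 4 to 5 | 1 | 5 | 4 |
| First dose to 1, then 3 to 4 (last end used) | 2 | 4 | 2 |

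The last row shows that a break in support within the initial stay is also counted as support. The SAP does not say whether the end is the last end or the end of each period. Taking each period from first dose and summing would give 1 + 4 = 5 days, more than the 4 days elapsed. That is the less natural reading.

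**Effect of delay.** Start from support running from 1.0 to 3.0: true 2.0, formula 3.0.

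- Same length, one day later (2.0 to 4.0): true 2.0, formula 4.0. The delay adds 1.0 day.
- Same end, one day later (2.0 to 3.0): true 1.0, formula 3.0. The 1.0 day of support avoided earns nothing.

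**Group mean.** Let p be the proportion of the analysed children who start support late within the initial stay, and d their mean wait. With one episode each, the mean is overstated by p × d.

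| p | d = 1 day | d = 2 days |
|---|---|---|
| 10% | 0.10 | 0.20 |
| 25% | 0.25 | 0.50 |
| 50% | 0.50 | 1.00 |

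**Difference between arms.** It shifts by p1·d1 − p0·d0. This is zero if the arms match. As an illustration only, p = 25% in both arms with waits of 2 and 1 days gives 0.25 × 2 − 0.25 × 1 = 0.25 day.

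**Ventilation.** Protocol 3.2, exclusion 1, bars children on invasive ventilation or expected to need it. Invasive support in an eligible child's initial stay should therefore begin after entry, and the overcount would generally apply. Protocol 8.9 also collects noninvasive support, which may already be running at first dose. If the SAP's variable includes it, the formula is right for that child so long as support is continuous.

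**The case against.** The strongest reply is that the definition is already correct and the formula was meant only to cut off oxygen given before first dose. On that view this is a drafting slip, and a programmer would see the intent. The intent is plausible, but the formula is explicit and unrestricted. Following it departs from the definition, and following the definition departs from the formula. Taking the later of first dose and start of support removes pre-dose use without the error.

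Several narrower points stand:

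- A child whose first support comes in a rehospitalisation is counted correctly, so only starts within the initial stay are affected.
- The SAP's count of new oxygen requirements also covers outpatients admitted later and increases in children already on oxygen. It is weak evidence of late starters here. The time-to-oxygen endpoint is the better evidence, and it shows that they are foreseen, not how many there will be.
- Given exclusion 1, few or no children may be invasively ventilated.
- The durations are descriptive, absent from the endpoint lists in Protocol 2.2.2 and SAP 3.2.2, and computed in a subset formed after randomisation. Even a corrected summary would not be a randomised comparison.

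These points limit the consequence. They do not reconcile the formula with the definition.

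**Conclusion.** The concern holds. As written, the initial-stay formula overstates duration for every child whose support starts after first dose in that stay. With a single episode the excess is exactly the wait; breaks in support are also counted as support. Children on continuous support from first dose are unaffected.

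The per-child result follows from the SAP's text alone. The group-level range, 0.10 to 1.00 day, rests wholly on the assumed proportions and waits. The ventilation part also rests on reading the lost signs as subtractions. No primary or listed secondary endpoint is touched, so this should be corrected but does not threaten the trial's main conclusions.

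**What to change.** In SAP 4.13.4, replace the initial-stay and rehospitalisation formulas with one rule for both oxygen and mechanical ventilation. For each period of support, duration is the end of support minus the later of first dose and the start of that period, summed over non-overlapping periods in the initial and any later hospitalisation. State the end time to use when support is still running at death, withdrawal or end of study; the definition already stops the count at end of study.

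The cost is about two sentences before database lock, plus that end-time clarification. No new data are needed. Start times are already required for the time-to-oxygen, time-to-ventilation and rehospitalisation calculations, and the SAP already has an imputation rule for missing ones.
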